8.2.6.3 Management of anemia

Close surveillance of any signs and symptoms is required: a routine blood hematology workup, including red blood cell (RBC) counts, hemoglobin, hematocrit, WBC with differential, and platelet counts will be done weekly during the first 2 cycles, and thereafter each treatment cycle before IMP administration. Patients should not start Cycle 1 treatment if hemoglobin is < 9.0 g/dL. To be eligible for the study and to receive the first study treatment, the participant must have been transfusion-free for 2 weeks. During the treatment period, erythrocyte transfusion can be given, upon Investigator decision. Erythropoietin can be given at the discretion of the Investigator, except during Screening and the first 2 cycles. Cycle delays or modifications should be compliant with Appendix 4 ([Section 10.4](#)).

8.2.6.4 Management of neutropenia

In patients who experienced either Grade 3 or 4 febrile neutropenia or Grade 4 decreased neutrophil count (< 500 cells/mm 3) for more than 1 week during study intervention, prophylactic G-CSF should be implemented per ASCO guidelines ([23](#)) to ensure dose intensity (Appendix 4 in [Section 10.4](#)). Doses of tusamitamab ravtansine should be reduced in case of recurrent events even after prophylactic G-CSF use.

If the patient continues to experience these reactions at a lowered dose, the treatment should be discontinued ([Section 7](#)).

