6.6.4 Dose adjustment/dose delay

Dose adjustment and/or cycle delay are permitted in case of adverse reaction. In case of toxicity, cycle delays and dose modifications should be implemented according to Appendix 4 ([Section 10.4](#)). Every effort will be made to administer the full dose regimen and maximize dose intensity.

Dose adjustments will be made according to the worst grade of adverse reaction observed within a cycle. If a participant experiences several adverse reactions and there are conflicting recommendations, the most conservative dose adjustment recommended should be followed.

Administration of the study treatment will be discontinued in the event of a TEAE that persists despite appropriate dose modifications or any other AE that, in the opinion of the Investigator, warrants discontinuation.

Pembrolizumab, ramucirumab or tusamitamab rvtansine can be discontinued prematurely. The patient will remain on study treatment until the last IMP can be discontinued until disease progression, unacceptable AE, or the participant's or investigator's decision to stop the treatment. The reason for premature discontinuation will be captured in the appropriate eCRF page.

Dose modifications different from those stated in the protocol should be made only in consultation with the Sponsor unless required for immediate participant safety.

All changes to study treatment administration must be recorded in the eCRF.

In the event of neutropenia, therapeutic G-CSF should be administered according to the current American Society of Clinical Oncology (ASCO) guidelines ([23](#)). In case of neutropenia or febrile neutropenia, prophylactic G-CSF should be started and in case of second episode beside prophylactic G-CSF, then dose should be reduced.

The acceptable treatment window for tusamitamab rvtansine and ramucirumab and pembrolizumab administration is ± 2 days for a Q2W (doublet cohort) and ± 3 days for a Q3W administration (triplet cohort).

See Appendix 4 in [Section 10.4](#) for further guidance in dose modification or discontinuation. Approved product label should be followed for patient receiving ramucirumab treatment for supportive care and dose modification requirement due to not listed adverse events. During the conduct of the study, second dose reduction may be needed, and need to be decided case by case discussion with the sponsor.

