Event	Symptoms severity (Nadir) (NCI CTCAE v5)	Management of IMP dosing (ramucirumab)	Management of IMP dosing (tusamitamab rfvansine)	Supportive care guidelines
Febrile neutropenia	Grade 3 Absolute neutrophil count <1000/mm ³ with a single temperature of >38.3°C (101°F) or a sustained temperature of ≥38°C (100.4°F) for more than 1 hour	Delay cycle until absolute neutrophil count >1500/mm ³ . 1st episode administer next cycle at the same dose and administer G-CSF 2nd episode: administer ramucirumab at reduce dose 3rd episode: definitive discontinuation	Delay cycle until absolute neutrophil count >1500/mm ³ . 1st episode administer next cycle at the same dose and administer G-CSF 2nd episode: administer tusamitamab rfvansine at reduce dose 3rd episode: definitive discontinuation	To ensure relative dose intensity, G-CSF is recommended as secondary prophylaxis in all patients with Grade 3 febrile neutropenia ASCO guideline is recommended for supportive treatment if there are no defined clinical standards (23)
	Grade 4 Life-threatening consequences	Administration changes to be decided at the Investigator's discretion per product label	Administration changes to be decided at the Investigator's discretion. 1st episode: administer next cycle at reduced dose and administer G-CSF 2nd episode: definitive discontinuation	
Hypertension	Grade 3 Severe hypertension	Withhold ramucirumab until controlled with medical management, and restart at same dose	Administer tusamitamab rfvansine as planned	
	Grade 4 Severe hypertension that cannot be controlled with antihypertensive therapy	Definitively discontinue ramucirumab	Administer tusamitamab rfvansine as planned	
Proteinuria	First occurrence of increased urine protein levels greater than or equal to 2 g per 24 hours	Omit ramucirumab until urine protein level is ≤2 g per 24 hours; then resume ramucirumab at a reduced dose (in doublet cohort, 8 mg at 1st episode, then 5 mg if 2nd episode and in triplet cohort, 8 mg at 1 st episode, then 6 mg if 2d episode)	Administer tusamitamab rfvansine as planned	
	Reoccurrence of urine protein level greater than 2 g per 24 hours following initial dose reduction	Omit ramucirumab until protein level is ≤2 g per 24 hours; then resume ramucirumab at a reduced dose:(6 mg or 5 mg)	Administer tusamitamab rfvansine as planned	

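### The protocol gives two different tusamitamab ravtansine sequences after a first Grade 4 febrile neutropenia: Appendix 4 reduces at once, while Sections 8.2.6.4 and 6.6.4 tie reduction to recurrence

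*Protocol*

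**What the plan says.** Three places in the protocol deal with tusamitamab ravtansine after febrile neutropenia.

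- **Appendix 4 (Section 10.4), febrile neutropenia, Grade 4 row.** The tusamitamab cell reads "1st episode: administer next cycle at reduced dose and administer G-CSF 2nd episode: definitive discontinuation". That sequence comes straight after a sentence leaving the decision to the investigator: "Administration changes to be decided at the Investigator's discretion. 1st episode: administer next cycle at reduced dose".
- **Section 8.2.6.4.** Its scope is stated as "In patients who experienced either Grade 3 or 4 febrile neutropenia or Grade 4 decreased neutrophil count" lasting more than a week. The first step is prophylactic G-CSF, given to preserve dose intensity. Then tusamitamab doses "should be reduced in case of recurrent events even after prophylactic G-CSF use". Finally: "If the patient continues to experience these reactions at a lowered dose, the treatment should be discontinued".
- **Section 6.6.4.** For neutropenia or febrile neutropenia, without grade, it starts prophylactic G-CSF, and "in case of second episode beside prophylactic G-CSF, then dose should be reduced". The sentence names no drug and no point of discontinuation. The same section says that dose modifications for toxicity follow Appendix 4.

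For comparison, the Appendix 4 row for Grade 3 febrile neutropenia keeps the dose and adds G-CSF after the first episode, then continues "2nd episode: administer tusamitamab rfvansine at reduce dose 3rd episode: definitive discontinuation".

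**The concern.** Section 8.2.6.4 cannot be read as a rule for Grade 3 alone, because it names Grade 4. A site that opens Section 8.2.6.4 after a first life-threatening episode finds G-CSF as the next step. A site that opens Appendix 4 finds a reduced dose plus G-CSF. The protocol allows only one tusamitamab reduction (Tables 11 and 12 in Section 6.6.4), so the episode at which that reduction is used also fixes the episode at which the drug must stop.

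Participant safety after a life-threatening event comes first. The statistical stake is smaller. For the doublet cohort, the SAP tabulates events leading to dose modification and to permanent discontinuation of tusamitamab (Section 4.7.2, Table 9), dose reductions and relative dose intensity (Section 4.7.1.2), and critical and major deviations (Section 4.2). If sites follow different sections, these outputs mix two management rules, and it is unclear which action would count as a deviation.

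**Working it through.** No calculation tests this point, so the check sets the three texts side by side for tusamitamab ravtansine.

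**Grade 4 febrile neutropenia**

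| Episode | Appendix 4, Grade 4 row | Section 8.2.6.4 | Section 6.6.4 |
|---|---|---|---|
| 1st | Reduced dose + G-CSF | G-CSF; reduction tied to recurrence | G-CSF |
| 2nd | Permanent stop | Reduced dose | Reduced dose |
| 3rd | Already stopped | Stop if events persist at the lower dose | Not stated in this sentence |
| Discretion | Opening sentence leaves changes to the investigator | None stated | Departures from the protocol need sponsor consultation, unless immediate safety requires them |

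**Where the divergence starts.** It starts in the first row. If the dose is reduced after episode 1, as in Appendix 4, episode 2 happens at a lowered dose, and Section 8.2.6.4 then also stops the drug. So does the text after Table 12 in Section 6.6.4, for an event that would call for a further tusamitamab reduction. If the dose is not reduced after episode 1, Section 8.2.6.4 reduces at episode 2 and stops at episode 3. One difference at episode 1 therefore moves permanent discontinuation from episode 3 to episode 2, a shift of 3 − 2 = 1 episode.

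**How far it extends**

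- Grade 3 febrile neutropenia: Appendix 4 gives same dose + G-CSF, then reduced dose, then stop. This agrees with Section 8.2.6.4.
- Grade 4 neutrophil decrease beyond 7 days: Appendix 4 gives same dose + growth factor, then reduced dose, then stop. This also agrees with Section 8.2.6.4.
- Ramucirumab after Grade 4 febrile neutropenia: the Appendix 4 cell defers to the investigator and the product label, so the episode conflict concerns tusamitamab only.

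**Scale for the tables.** The documents give no rate for the event. With about 36 treated participants in the doublet cohort (Section 9.2), one participant classified differently moves a percentage by 1/36 = 2.8 percentage points.

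**The case against.** The best defence is that Appendix 4 governs. Section 6.6.4 sends dose modifications there and adjusts by the worst grade in the cycle, which points to a graded table. The lead-in to Section 8.2.6 says that management of events related to all three drugs is summarised in Appendix 4 and calls its own summaries a reminder. Section 8.2.6.4 also cites the appendix. These pointers favour the table, but they do not remove the conflict. Sections 6.6.4 and 8.2.6.4 each go on to state a different rule. In Section 8.2.6.4 the citation sits in the G-CSF sentence, not in the sentences on reduction and stopping. The anemia and neuropathy sections (8.2.6.3 and 8.2.6.10) expressly require modifications to comply with Appendix 4; the neutropenia section has no such sentence. The tie-break in Section 6.6.4 towards the stricter adjustment covers a participant with several reactions, not two rules for one reaction.

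A second defence is that these are guidelines and the Grade 4 cell allows discretion. That cell also fixes an episode sequence, and does not say how the two fit together.

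Part of the objection stands, and it limits three stronger readings:

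- A reader might infer two independent contradictions, one at each of the first two episodes. The gap with Section 8.2.6.4 at the second episode follows from the first.
- A reader might infer that Section 6.6.4 repeats Section 8.2.6.4. Its neutropenia sentence has no grade, drug or discontinuation step.
- A reader might infer that sites will in fact diverge. The documents show that they could, not that they will.

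**Conclusion.** The inconsistency is real and narrow. For tusamitamab ravtansine after a first Grade 4 febrile neutropenia, the protocol offers two sequences that part at the first episode and place permanent discontinuation one episode apart. The discretion sentence in Appendix 4 adds to the ambiguity.

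This rests on the plain sense of Sections 8.2.6.4 and 6.6.4. Neither says that reduction happens only on recurrence, but both give G-CSF as the first step and attach reduction to a later episode.

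The consequence is a risk of uneven management after a life-threatening event, with some blurring of descriptive safety and exposure tables. Its frequency is unknown, because no event rate is given. The documents do not support a claim of harm to the primary endpoints. Whether neutropenia complicated by fever counts as a DLT is decided by Table 5 and the Study Committee, not by later dosing, and no effect on response rate is shown.

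**What to change.** The sponsor should reconcile Section 6.6.4, Section 8.2.6.4 and the Grade 4 febrile neutropenia row of Appendix 4 to one episode-by-episode sequence for tusamitamab ravtansine. The text should say how the investigator-discretion sentence relates to that sequence. If Appendix 4 is meant to prevail, Sections 6.6.4 and 8.2.6.4 should say so and drop or align their own rules. No view is offered here on which sequence is right.

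The cost is protocol wording only. Sample size, endpoints and SAP methods are unaffected.

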8.2.6.5 Liver function tests

Hepatic enzyme increase has been reported with tusamitamab ravtansine administration as monotherapy or ramucirumab. Patients should be carefully followed and in case of Grade ≥ 3 abnormal liver function tests, additional liver function tests will be done every 2 to 3 days until recovery to baseline value. Tusamitamab ravtansine should be permanently discontinued in case of drug-induced Grade 4 liver enzyme increase. For stopping rules for ramucirumab administration, the current product leaflet should be followed.

Grade ≥ 3 (ie, $> 5 \times$ ULN) increased liver enzyme events should be reported as AESIs.

8.2.6.6 *Hypertension*

An increased incidence of severe hypertension (CTCAE Grade 3) has been reported in patients receiving ramucirumab as compared with placebo. In most cases, hypertension was controlled using standard antihypertensive treatment. Preexisting hypertension should be controlled before starting ramucirumab treatment. Monitoring of blood pressure is required during ramucirumab therapy. Every attempt should be made to control blood pressure to systolic <140 mmHg and diastolic <90 mmHg prior to starting treatment with ramucirumab. Routine clinical and laboratory monitoring is required in patients who again develop hypertension or experience a deterioration in previous hypertension.

Withhold ramucirumab for severe hypertension until medically controlled. Permanently discontinue ramucirumab for medically significant hypertension that cannot be controlled with antihypertensive therapy or in patients with hypertensive crisis or hypertensive encephalopathy.

8.2.6.7 *Proteinuria*

Proteinuria is an adverse effect for all therapies targeting the vascular endothelial growth factor (VEGF)/VEGFR-2 pathway, including ramucirumab. Proteinuria has been associated with ramucirumab in clinical studies; the majority of events were Grade 1 or 2.

Monitor proteinuria by urine dipstick and/or urinary protein creatinine ratio. If the result of the urine dipstick is 2+ or greater, perform a 24 hours urine collection for protein measurement.

Withhold ramucirumab for urine protein levels of 2 or more grams collected over 24 hours. Reinitiate ramucirumab at a reduced dose once the urine protein level returns to less than 2 grams over 24 hours. Permanently discontinue ramucirumab for urine protein levels greater than 3 grams over 24 hours, or in the setting of nephrotic syndrome.

8.2.6.8 *Bleeding/Hemorrhage*

Ramucirumab is an antiangiogenic therapy and has the potential to increase the risk of severe bleeding. Permanently discontinue ramucirumab in patients who experience severe (Grade 3 or Grade 4) bleeding.

8.2.6.9 *Arterial Thromboembolic Events*

Serious, sometimes fatal, arterial thromboembolic events (ATEs), including myocardial infarction, cardiac arrest, cerebrovascular accident, and cerebral ischemia, occurred across clinical trials. Permanently discontinue ramucirumab in patients who experience an ATE.

8.2.6.10 *Peripheral neuropathy*

Participants with a known history of peripheral neuropathies and/or patients having received medications known to cause peripheral neuropathies (eg, prior antitubulin, platinum and/or taxanes) are at high risk of developing neuropathy. Peripheral neuropathies potentially present as signs and symptoms of sensory (paresthesia, dysesthesias, pain, and change in proprioception), motor (weakness), and neural dysfunctions.

There is no further recommendation beyond routine guidance on prevention and treatment of peripheral neuropathy. Cycle delays or modifications should be compliant with Appendix 4 ([Section 10.4](#)).

8.2.6.11 Colitis (including hemorrhagic)

In study TED13751 evaluating tusamitamab ravtansine in patients with several cancer types, a limited number of participants developed colitis. Based on clinical observations, patients with known underlying colitis or gastrointestinal tract conditions are noted to be at highest risk for such events. The monitoring of patients for GI toxicities will rely on careful evaluation by routine history, physical examination, and standard laboratory examination. Close surveillance of any signs and symptoms is required, with additional routine hematology workup (hemoglobin, hematocrit, and WBC with differential and platelet counts) whenever indicated. As 1 case of Grade 4 erosive colitis has been reported, it is recommended to conduct close surveillance of any diarrhea event, with further exams when clinically indicated. Treatment is per patient condition, based on Investigator discretion.

8.2.7 Immune-related adverse reactions

Immune-related adverse reactions are provided in Appendix 4 ([Section 10.4](#)).

8.3 ADVERSE EVENTS AND SERIOUS ADVERSE EVENTS

8.3.1 Adverse events, treatment-emergent adverse events, and adverse events of special interest

The safety profile of the IMP will be based on incidence, severity (as graded by the NCI CTCAE V5.0), and cumulative nature of TEAEs. TEAEs are defined as AEs that develop, worsen or become serious during the on-treatment period. For this study, the on-treatment period will be defined as the period from the time of first dose of IMP to at least Day 30 of the last tusamitamab ravtansine administration. Each patient will be assessed preferably by the same physician for AEs and according to the NCI CTCAE V5.0 classification.

An AESI is an AE (serious or nonserious) of scientific and medical concern specific to the Sponsor's product or program, for which ongoing monitoring and immediate notification by the Investigator to the Sponsor is required. Such events may require further investigation in order to characterize and understand them. Adverse events of special interest may be added, modified or removed during a study by protocol amendment.

- Pregnancy of a female subject entered in a study as well as pregnancy occurring in a female partner of a male subject entered in a study with IMP/NIMP;
 - Pregnancy occurring in a female participant entered in the clinical trial or in a female partner of a male participant entered in the clinical trial. It will be qualified as an SAE only if it fulfills one of the seriousness criteria (see Appendix 3 [[Section 10.3](#)]).
 - In the event of pregnancy in a female participant, IMP should be discontinued.

- Follow-up of the pregnancy in a female participant or in a female partner of a male participant is mandatory until the outcome has been determined (See Appendix 5 [Section 10.5]).
- Grade ≥ 3 keratopathy
- Bundle branch blocks or any conduction defects.
- Grade ≥ 3 liver enzyme increased (symptomatic or asymptomatic)
- Symptomatic overdose (serious or nonserious) with IMP/NIMP
 - An overdose (accidental or intentional) with the IMP/NIMP is an event suspected by the Investigator or spontaneously notified by the participant and defined as at least 30% above the intended administered dose at each cycle expressed in unit per body surface or unit per weight.
- All protocol-defined DLT (Section 4.1).

The definitions of an AE or SAE can be found in Appendix 3 (Section 10.3).

Adverse events will be reported by the participant (or, when appropriate, by a caregiver, surrogate, or the participant's legally authorized representative).

The Investigator and any qualified designees are responsible for detecting, documenting, and recording events that meet the definition of an AE or SAE and remain responsible for following up AEs that are serious, considered related to the study intervention or study procedures, or that caused the participant to discontinue the study intervention (see Section 7).

8.3.2 Time period and frequency for collecting AE and SAE information

All SAEs will be collected from the signing of the screening ICF at the time points specified in the SOA (Section 1.3) and until at least 30 days after the last study intervention administration.

All AEs will be collected from the signing of the screening ICF at the time points specified in the SOA (Section 1.3) and until at least 30 days after the last study intervention administration.

For participant who was prescreened and had fresh biopsy, only the Adverse Events related to the fresh biopsy procedure itself should also be reported in eCRF as general requirement of AE/SAE with the reporting time frame interval of 1 month for prescreening period after fresh biopsy. All SAEs and AESI will be recorded and reported to the Sponsor or designee immediately and under no circumstance should this exceed 24 hours, as indicated in Appendix 3 (Section 10.3). The Investigator will submit any updated SAE data to the Sponsor within 24 hours of it being available.

Investigators are not obligated to actively seek AE or SAE after the conclusion of study participation. However, if the Investigator learns of any SAE, including a death, at any time after a participant has been discharged from the study, and he/she considers the event to be reasonably related to the study intervention or study participation, the Investigator must promptly notify the Sponsor.

During the follow-up period, SAEs (regardless of relationship to IMP) ongoing at the end of study treatment and IMP-related AEs ongoing at the end of study treatment, as well as new IMP-related AE/SAEs, will be followed until resolution or stabilization.

8.3.3 Method of detecting AEs and SAEs

The method of recording, evaluating, and assessing causality of AE and SAE and the procedures for completing and transmitting SAE reports are provided in Appendix 3 ([Section 10.3](#)).

Care will be taken not to introduce bias when detecting AEs and/or SAEs. Open-ended and non-leading verbal questioning of the participant is the preferred method to inquire about AE occurrences.

8.3.4 Follow-up of AEs and SAEs

After the initial AE/AESI/SAE report, the Investigator is required to proactively follow each participant at subsequent visits/contacts. At the pre-specified study end-date, all SAEs, and nonserious AESIs (as defined in [Section 8.3.1](#)), will be followed until resolution, stabilization, the event is otherwise explained, or the participant is lost to follow-up (as defined in [Section 7.3](#)). Further information on follow-up procedures is given in Appendix 3 ([Section 10.3](#)).

